#### **SCHEMA**

Immunogenicity of Nonavalent HPV Vaccine Administered Prior To Renal Transplantation in Adults: A Prospective, Single-Arm, Multi-Center Clinical Trial

\*\* [NOTE: For COVID-19 Contingency Plan, please see Appendix G and Appendix H]

## 1. OBJECTIVES

The objective of this prospective single-arm trial is to evaluate if the Gardasil® 9 HPV vaccine induces and sustains an adequate immune response at 12-months post-transplantation among 18-49 year old kidney transplant recipients when  $\geq 1$  doses of the vaccine are administered prior to transplantation.

# 1.1 Primary Objectives

To assess HPV vaccine-type-specific seroconversion rates at 12-months post-transplantation among kidney transplant recipients who receive  $\geq 1$  doses of the Gardasil® 9 HPV vaccine  $\geq 30$  days prior to transplantation.

# 1.2 Secondary Objectives

To assess HPV vaccine-type-specific seroconversion rates at 6- and 12-months post-transplantation stratified by number of doses (1, 2, or 3) of the vaccine given pre-transplant among kidney transplant recipients who receive ≥ 1 doses of the Gardasil® 9 HPV vaccine prior to transplantation:

# 1.3 Exploratory Objectives

To assess the following among kidney transplant recipients who receive  $\geq 1$  doses of the Gardasil® 9 HPV vaccine  $\geq 30$  days prior to transplantation:

- 1) HPV vaccine-type-specific seroconversion rates at 12-months post-transplantation stratified by:
  - a) time elapsed between last vaccine dose and the transplant procedure;
  - b) variations in dosing and types of post-transplant immunosuppressant medications; and interactions with type of transplant surgery (living donor/deceased donor);
  - c) differences in Human Leukocyte Antigen (HLA) histocompatibility between donor and recipient;
  - d) differences in biological sex (i.e. male vs. female) of the transplant recipient.
- 2) Stability of HPV vaccine-type-specific geometric mean titers (GMT) at 6 and 12-months post-transplantation and rise in HPV vaccine-type-specific GMT at the 13-month post-transplant visit.
- 3) Vaccine safety profile and allograft rejection/opportunistic infections stratified by number of vaccine doses and time between the last vaccine dose and the transplant procedure.
- 4) HPV detection in samples from the cervix/vagina and oral cavity at baseline (pre-vaccination) and at 6- and 12-months post-vaccination, overall and by number of vaccine doses (1, 2, or 3), sexual behavior, type-specific seroconversion rates, and time elapsed between the last vaccine dose and the transplant procedure.

## 2. BACKGROUND

# 2.1 Study Disease

Adult solid organ transplant recipients are at increased risk of developing several types of malignant tumors related to the use of immunosuppression to prevent transplant rejection [1]. Cancers causally linked to infections with carcinogenic human papillomavirus (HPV) genotypes, including squamous cell carcinomas of the anogenital region and oropharynx, are among the higher incidence cancers in this group

and potentially the most preventable [2-4]. The number of solid organ transplant recipients has increased along with their post-transplant lifespan. As such, the need for prevention of HPV-associated cancers is projected to increase [5].

## 2.2 Study Agent

Gardasil® 9 Human Papillomavirus vaccine is a non-infectious recombinant 9-valent vaccine prepared from the purified virus-like particles (VLPs) of the major capsid (L1) protein of HPV Types 6, 11, 16, 18, 31, 33, 45, 52, and 58. The L1 proteins are produced by separate fermentations using recombinant *Saccharomyces cerevisiae* and self-assembled into VLPs. The fermentation process involves growth of *S. cerevisiae* on chemically-defined fermentation media which include vitamins, amino acids, mineral salts, and carbohydrates. The VLPs are released from the yeast cells by cell disruption and purified by a series of chemical and physical methods. The purified VLPs are adsorbed on preformed aluminum-containing adjuvant (Amorphous Aluminum Hydroxyphosphate Sulfate or AAHS). The 9-valent HPV VLP vaccine is a sterile liquid suspension that is prepared by combining the adsorbed VLPs of each HPV type and additional amounts of the aluminum-containing adjuvant and the final purification buffer [6].

Gardasil® 9 is indicated for prevention of cervical, vulvar, vaginal, and anal cancers caused by HPV types 16, 18, 31, 33, 45, 52 and 58; and for the prevention of genital warts caused by HPV types 6 or 11; in females 9-26 years of age. Gardasil® 9 also adds protection against precancerous or dysplastic cervical, vulvar, vaginal, and anal lesions caused by the covered HPV types.

The safety of Gardasil® 9 was evaluated in six clinical studies that included 13,234 individuals who received at least one dose and had safety follow-up. The most common (≥ 10%) local and systemic adverse reactions of the Gardasil® 9 HPV vaccine in females and males 16 through 26 years of age were injection site pain (90%, 63%), injection site swelling (40%, 20%), injection site erythema (34%, 21%), and headache (15%, 7%). Pyrexia may be experienced by 5% of female vaccine recipients and 2% for male vaccine recipients. Contraindications include hypersensitivity, including severe allergic reactions to yeast (a vaccine component), or after a previous Gardasil® dose [6]. Individuals who develop symptoms indicative of hypersensitivity after the first dose should not receive additional doses. Syncope, sometimes associated with tonic-clonic movements and other seizure-like activity, has been reported following HPV vaccination. Participants must be monitored for 30 minutes following vaccination for syncope/convulsive syncope and allergic reactions. There have been no adequate and well-controlled studies of Gardasil® 9 in pregnant women. The Gardasil® 9 HPV vaccine is not recommended for pregnant women.

# 2.3 Rationale

The nonavalent Gardasil® 9 prophylactic HPV vaccine is nearly 100% efficacious in preventing infection with the seven carcinogenic (HPV 16, 18, 31, 33, 45, 52, 58) and two condyloma-inducing viruses (HPV 6, 11) when given to individuals who have not been exposed to these specific HPV types. The body of evidence [41-45] that has influenced the current approval of Gardasil® 9 by the US Food and Drug Administration (FDA) for ages 9-45 years in both females and males include:

- clinical trial data about clinical efficacy of Gardasil® 9 (endpoints such as persistent infection, genital warts, and precancerous lesions related to HPV types covered by the vaccine) in 16-26 years old women and men;
- (ii) inferential data from clinical trial data about clinical efficacy of quadrivalent Gardasil® prophylactic HPV vaccine (the forerunner to Gardasil® 9 with a similar manufacturing process) in 27-45 years old women for the four key HPV types (HPV 16, 18, 6 & 11) covered by both the quadrivalent and nonvalent vaccines
- (iii) immunogenicity and immunobridging data (i.e., inferring efficacy based on similar or higher vaccine-induced serologic immune titers in age-groups where efficacy has not been directly studied, e.g., individuals <16 years at vaccination, or men 27-45 years)

The protective effect of Gardasil® 9 among older immunosuppressed adults is unknown. Given the continued HPV-related risk in the post-transplant years (evidenced by a high proportion of women and men testing positive for cervical/anogenital HPV DNA [7], even with no additional sexual acquisition risk of new HPV infections, it is speculated that this represents a consequence of activation of latent HPV infections. Empirical studies to demonstrate the phenomenon of reactivation of HPV infection and the effect of HPV vaccination on this purported phenomenon are lacking.

Guidelines from both the Centers for Disease Control and prevention (CDC) and American Society of Transplantation recommend that immunosuppressed individuals, including transplant candidates, receive the same HPV vaccines according to the same schedule as individuals in the general population [8,9]. Only two small observational immunogenicity studies have evaluated post-transplantation serologic responses to the quadrivalent Gardasil® vaccine [10,11]. Although the safety of the virus-like particle (VLP)-based subunit HPV vaccines has not been a major concern, the strength of the immunologic responses (and consequent efficacy) among immunosuppressed transplant recipients remains uncertain [5,12]. Research questions related to the efficacy of the prophylactic HPV vaccination among adult solid organ transplant candidates and recipients include the levels and inter-person variability of peak and plateau antibody titers and avidity of antibody responses, as well as the optimal timing of vaccine administration either pre- or post-transplant. The possibility that reactivation or latent HPV infection may occur with immunosuppression is supported by descriptive clinical studies, but the potential of vaccination to suppress this reactivation is untested. The relationship between HPV vaccine response and post-transplantation immune status measurements – both non-specific immune monitoring assays, as well as opportunistic pathogen-specific response assays – is unclear and merits further exploration [13]. Renal transplant candidates represent an ideal population in which to evaluate prophylactic vaccine efficacy in organ transplant recipients because many such transplants are planned months in advance, and patients have frequent medical contacts, facilitating recruitment and required visits.

Given the strong biological rationale, a recently convened International Agency for Research on Cancer/National Cancer Institute workshop has recommended seroconversion, and specifically immunological non-inferiority, as sufficient for a presumption of efficacy for the HPV vaccine in immunobridging studies focused on the expansion of vaccine indications [14]. Thus, the endpoint for this trial is seroconversion, and we will define efficacy as greater than or equal to 90% of the study population achieving seroconversion. The definition for positivity, or seroconversion, will be based on results of the HPV-9 cLIA (Merck) or, alternatively, a validated 9-valent HPV multiplex assay developed at the NCI Frederick National Laboratory for Cancer Research (FNLCR), which measures HPV type-specific antibodies to neutralizing epitopes on VLPs from a patient's serum sample. Seropositivity is not part of the eligibility criteria for enrollment.

# Vaccine Doses and Timing in relation to Transplant Surgery and Immunosuppression.

Current (2018) CDC recommendations suggest that Gardasil® 9 be given in a 3-dose schedule at 0, 2, and 6 months for immunocompromised individuals (such as transplant recipients) between the ages of 16 and 45 years. (There are no recommendations for vaccination for individuals over 45 years of age, and such use is considered off-label.) Furthermore, there are no recommendations on the optimal number and timing of doses in relation to the transplant surgery. This trial will seek to enroll both living-donor and deceased-donor transplant recipients, and the number and timing of vaccine doses will be dependent on two factors:

- i. The time remaining between enrollment date and transplant surgery.
- ii. Need for avoiding administering any vaccine doses for at least 12 months in the post-transplant period when the strongest regimens of immunosuppressive medications to prevent transplant rejection are being administered.

Due to these caveats, participants may receive one, two, or three doses of vaccines prior to transplant. If all three doses are not administered before transplant then the rest of the doses in the three dose vaccine

series will be administered at or after 12-months after transplant. An abbreviated schedule of vaccination (permitted by current vaccine label/CDC recommendations) may also be utilized to allow administration of as many vaccine doses prior to transplantation as possible. If participants do not undergo transplant surgery within 12 months of study enrollment and have not received the recommended three dose series in the intervening 12 months, the remaining doses will be offered via Additional Study Visit(s) at 12 months and, if necessary, at 15 months after the first vaccine dose.

**Desensitization.** Both vaccines and infections are known to cause both humoral and cellular immune activation, which is of particular interest in transplant populations because alloreactive T-cells and the development of anti-HLA antibodies mediate transplant allograft injury. Transplant recipients who are already highly sensitized to alloantigens are at higher risk for rebound immune activation through a process called heterologous immunity, potentially leading to allograft injury. Furthermore, the potential for a 'shared epitope' between viral products and Human Leukocyte Antigen (HLA) proteins suggests that vaccination can produce *de novo* HLA antibody formation [15]. Desensitization procedures vary somewhat among the five participating transplant centers, which does not permit proposing uniform criteria across all study sites for determining exclusion due to desensitization. In general, adults who have received a prior transplant, have unsuitable scores on Calculated Panel Reactive Antibody (PRA) percentage (institution-specific thresholds), or an ABO incompatible donor are likely to undergo desensitization at one or more of the study centers. These factors, among others, will be used by the study clinician to determine exclusion due to anticipated desensitization in the study.

**HPV Vaccination and Risk of Allograft Rejection.** Current recommendations allow for HPV vaccine administration before or after transplantation, and that it is safe to do so because it is not a live vaccine [16]. Studies that have examined safety of the vaccine in the post-transplant setting have reported no elevation in rejection episodes attributed to the vaccine [10,11].

Sexual Behavior, Detectable HPV Infection, and Vaccine-Induced Seroconversion. The possibility that reactivation of latent HPV infection may occur with immunosuppression is supported by descriptive clinical studies, but the potential of vaccination to suppress this reactivation is untested. Only a few studies have examined the prevalence of oral/anal/genital HPV in renal transplant recipients, generally following transplant [17]. The first longitudinal study of cervical-vaginal HPV prevalence before and after renal transplant found an increase from 19% pre-transplant to 31% post-transplant [18]. This increase occurred in the absence of reported changes in sexual behavior, suggesting re-activation of latent viral infection. Although the clinical impact of these findings are presently uncertain, an increased prevalence of cervical-vaginal HPV in the absence of person-to-person transmission has implications for patient management [19]. This will be the first study among renal transplant recipients to show whether there is a difference in Gardasil® 9-associated seroconversion between individuals with detectable versus undetectable HPV infections (cervical-vaginal and oral) that cannot be explained by sexual behavior.

**Hypothesis:** The Gardasil® 9 nonavalent vaccine given before the solid organ transplant procedure will induce and maintain adequate immunogenicity in the post-transplant period despite immunosuppression.

# 3. SUMMARY OF STUDY PLAN

**Design Overview.** This will be a prospective single-arm trial to evaluate if the Gardasil® 9 HPV vaccine induces and sustains an adequate immune response at 12-months post-transplantation among 18-49 years old kidney transplant recipients when ≥ 1 doses of the vaccine are administered prior to transplantation (see Schema). The study population will include candidates who are scheduled to undergo kidney transplant within 12 months of enrollment at five transplant centers in the United States: Cedars-Sinai Medical Center (CSMC); the University of California, San Francisco Medical Center (UCSF); Northwestern University Feinberg School of Medicine (NW); University of Alabama at Birmingham (UAB); and the University of North Carolina at Chapel Hill (UNC). The local study teams at the clinical sites, which include transplant infectious disease specialists, transplant nephrologists, and transplant surgeons, will determine each

potential participant's eligibility for the study based on chart review and patient history. Prior to enrollment, women who are able to become pregnant will be required to have a negative pregnancy test and agree to the use of contraception or abstinence for the study period.

Screening of Potential Participants: Potential participants will be identified through clinical encounters in the transplant clinic, review of medical charts, review of transplant waiting lists, and review of upcoming transplants and donor evaluations. Renal transplant candidates on institutional waitlist for a deceased donor renal transplant expected to receive a kidney within 12 months, or currently having a potential living donor undergoing workup in anticipation of a living donor transplant, will be reviewed for eligibility.

**Pre-transplant work-up and vaccinations**: The timing of vaccination in relation to the transplant surgery are considered in relation to several factors. The time available between enrollment and the transplant surgery and the feasibility of study visits in the pre-transplant period will vary by type of surgery (living donor versus deceased donor transplant). Further, the possibility of integrating with the schedule for pre-transplant clinical work-up or visiting for a study-specific purpose alone will vary by the clinical condition of the potential participants and the institutional transplant center visit requirements for every clinic site. All enrolled participants are expected to receive at least 1 dose of the vaccine prior to transplant surgery with at least 30-days between the first dose and transplant surgery. There are specific CDC recommendations about the minimum time between doses which will affect when the second and third doses are administered (see section 5.1). Other than requiring adherence to these minimum intervals (within +/- 2 weeks), the protocol will not mandate specific time windows for receiving the vaccine, considering challenges of accrual/retention in the study. Transplant candidates are typically burdened with ongoing pre-transplant clinical issues and have non-uniform follow-up visit schedules. Study staff will attempt to maximize opportunities for coordinating study-related visits on the same day as scheduled transplant-related/clinical care-related visits. However, the timing of transplant surgery is dependent on a range of factors, several of which are unpredictable at the time of study enrollment. Therefore, not all participants in the study may be able to receive all three doses of the vaccine prior to transplant. In fact, the second and third doses can be administered in the pre-transplant period or be administered at or after 12-months post-transplant.

With a few exceptions (see below), most participants will undergo the following study visits based on the number of doses that might be able to be administered prior to surgery:

	Participant is able to complete only 1 dose prior to surgery	Participant is able to complete 2 doses prior to surgery	Participant is able to complete 3 doses prior to surgery	
Consent and Screening Visit	Consent	Consent	Consent	
Pre-Transplant Vaccine Visit 1	Vaccine #1 & specimen collection	Vaccine #1 & specimen collection	Vaccine #1 & specimen collection	
Pre-Transplant Vaccine Visit 2	~~	Vaccine #2 & specimen collection	Vaccine #2 & specimen collection	
Pre-Transplant Vaccine Visit 3	~~	~~	Vaccine #3 & specimen collection	
Transplant Surgery	Occurs; specimen collection	Occurs; no research procedures	Occurs; no research procedures	
6 Month Post-Transplant Visit	Specimen collection	Specimen collection	Specimen collection	
12 Month Post-Transplant Visit	Vaccine #2 & specimen collection	Vaccine #3 & specimen collection	Specimen collection	
13 Month Post-Transplant Visit	Specimen collection	Specimen collection	~~	
Additional Study Visit 1	Vaccine #3	~~	~~	

\*Specific details regarding the timing of study visits can be found in Appendix B.

There might be situations when a transplant surgery is scheduled within a few weeks after the first, second, or third doses, but it gets postponed/rescheduled/cancelled. Although study staff will attempt to complete the remaining doses in the 12-months post-enrollment period, there might be situations, albeit uncommon, where the transplant surgery does not occur within 12-months of enrollment and the participants are not able to complete all vaccine study visits. In such situations, participants who have received only one or two doses will be offered two or one Additional Study visit(s) to complete the three-dose series and will be considered and notified that they will be off-study (See Section 8.4). The Additional Study Visit 1 will occur 12 months (±2 weeks) after Pre-Transplant Vaccine Visit 1, and Additional Study Visit 2 will occur 3 months (+4 weeks) after Additional Study Visit 1. Also, participants who have completed all three doses but their transplant surgery gets postponed/rescheduled and eventually does not occur within 12-months of enrollment will be considered off-study. The three possible scenarios discussed above will have the study visit schedule as illustrated below:

	Participant completes 1 dose, but transplant does not occur within 12 months of enrollment	Participant completes 2 doses, but transplant does not occur within 12 months of enrollment	Participant completes 3 doses, but transplant does not occur within 12 months of enrollment	
Consent and Screening Visit	Consent	Consent	Consent	
Pre-Transplant Vaccine Visit 1	Vaccine #1 & specimen collection	Vaccine #1 & specimen collection	Vaccine #1 & specimen collection	
Pre-Transplant Vaccine Visit 2	~~	Vaccine #2 & specimen collection	Vaccine #2 & specimen collection	
Pre-Transplant Vaccine Visit 3	~~	~	Vaccine #3 & specimen collection	
Transplant Surgery	Does not occur	Does not occur	Does not occur	
6 Month Post-Transplant Visit	~~	~~	~~	
12 Month Post-Transplant Visit	~~	~~	~~	
13 Month Post-Transplant Visit	~~	~~	~~	
Additional Study Visit 1	Vaccine #2 & specimen collection	Vaccine #3 & specimen collection	~~	
Additional Study Visit 2	Vaccine #3	~	~~	

\*Specific details regarding the timing of study visits can be found in Appendix B.

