# 5.1 Dose Regimen and Dose Groups

- Agent: Gardasil® 9 nonavalent HPV vaccine
- Dose and regimen for agent: 0.5 mL single-dose for intramuscular administration
- Duration for agent: Gardasil® 9 must be administered according to the following requirements:
  - o Dose 1:  $\ge$  30 days prior to transplant
  - o Dose 2:  $\geq$  30 days after Dose 1
  - Dose 3:  $\geq$ 5 months after Dose 1 AND  $\geq$  3 months after Dose 2
- All participants will be offered the entire 3-dose series. Due to differences in the timing of
  transplant surgery, the feasibility of additional study-related visits prior to transplant surgery, and
  the possibility that transplant surgery will not occur within 12 months of enrollment, there are six
  different dosing schedules, outlined in Table 2 below.

Table 2. Dose Regimens

	Participant is able to complete only 1 dose prior to surgery	Participant is able to complete 2 doses prior to surgery	Participant is able to complete 3 doses prior to surgery	Participant completes 1 dose, but transplant does not occur within 12 months of enrollment	Participant completes 2 doses, but transplant does not occur within 12 months of enrollment	Participant completes 3 doses, but transplant does not occur within 12 months of enrollment
Dose 1		≥	30 days prior to	Transplant Surge	гу	
Dose 2	12 months (±2 weeks) after Transplant Surgery  12 months ≥30 days after Dose 1		≥30 days after Dose 1	12 months (±2 weeks) after Dose 1	≥30 days after Dose 1	≥30 days after Dose 1
Dose 3	3 months (+4 weeks) after Dose 2	12 months (±2 weeks) after Transplant Surgery	≥5 months after Dose 1 AND ≥3 months after Dose 2	3 months (+4 weeks) after Dose 2	12 months (±2 weeks) after Dose 2	≥5 months after Dose 1 AND ≥3 months after Dose 2

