- Participants who receive only one dose prior to transplant and second dose at the 12 Month Post-Transplant
  Visit will be offered an Additional Study Visit at 3 months (+4 weeks) after 12 Month Post-Transplant
  Visit
- Participants who receive one vaccine dose, but their transplant surgery is postponed/rescheduled/cancelled and eventually not scheduled within 12 months of the study enrollment date, will be offered two Additional Study Visits to complete the three dose vaccine series. Additional Study Visit 1 will occur 12 months (±2 weeks) after Pre-Transplant Vaccine Visit 1, and Additional Study Visit 2 will occur 3 months (±4 weeks) after Additional Study Visit 1.

<sup>2 Pre-Transplant Vaccine Visits 1 and 2 are optional, guided by the timing of surgery and feasibility of additional study-related visits. Participants who do not have Pre-Transplant Vaccine Visits 1 and/or 2 will still receive the complete 3-dose series of the vaccine (the remaining vaccination(s) will occur post-transplant; see Appendix B for a detailed schedule). If the Pre-Transplant Vaccine Visits 1 and 2 occur, the following intervals must be used:

<sup>3 The 6 Month Post-Transplant Visit will occur 6 months (±2 weeks) after the participant's renal transplant procedure.

<sup>4 The 12 Month Post-Transplant Visit will occur 12 months (±2 weeks) after the participant's renal transplant procedure.

<sup>5 The 13 Month Post-Transplant Visit will occur 1 month (+2 weeks) after the 12 Month Post-Transplant Visit. This visit will occur only for participants who received a vaccine at the 12 Month Post-Vaccine Visit.

<sup>6 Additional Study Visit(s) will be offered for participants only for the purpose of completing their vaccine series (second and/or third doses) in the following scenarios:

- Participants who receive two vaccine doses, but their transplant surgery does not occur within 12 months of the study enrollment date, will complete an Additional Study Visit to complete the three dose vaccine series at 12 months (±2 weeks) after Pre-Transplant Vaccine Visit 1.

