## 7.6 Additional Study Visit(s)

Additional Study Visits will be offered only for the purpose of completing the vaccine series for participants who are unable to receive their second or third vaccine doses in accordance to the proposed schedule of events. These Visits will be offered in the following scenarios:

- 1. Participants who only received one dose prior to transplant, and their second dose administered at 12 Month Post-Transplant Visit. These participants will receive their third dose at an Additional Study Visit 3 months (+4 weeks) after the 12 Month Post-Transplant Visit.
- 2. Participants who received two vaccine doses prior to transplant, but their transplant surgery is postponed/rescheduled/cancelled and eventually not scheduled within 12 months of the study enrollment date, will complete their three dose vaccine series at an Additional Study Visit at 12 months (±2 weeks) after Pre-Transplant Vaccine Visit 1. These participants will be considered off-study after the Additional Study Visit is completed, and follow-up calls were made, as

- discussed in Section 8.4.
- 3. Participants who receive one vaccine dose prior to transplant, but their transplant surgery does not occur within 12 months of Pre-Transplant Vaccine Visit 1, will be offered two Additional Study Visits to complete the three dose vaccine series. Additional Study Visit 1 will occur 12 months (±2 weeks) after the Pre-Transplant Vaccine Visit 1. Additional Study Visit 2 will occur 3 months (+4 weeks) after Additional Study Visit 2. These participants will be considered offstudy after the Additional Study Visits are completed, and follow-up phone calls were made, as discussed in Section 8.4.

The following procedures will be performed during the Additional Study Visits:

1) The second or third dose of Gardasil® 9 is administered.

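### Dose 3 for two-dose participants not transplanted within 12 months: Table 2 counts from Dose 2, five other places count from Dose 1, and the Dose 1 date can break the 3-month minimum

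*Combined protocol and SAP*

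**What the plan says.** The point concerns participants who have received two doses and whose transplant does not take place within 12 months of enrollment.

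- **Section 5.1, Table 2** (fifth column, Dose 3 row): "12 months (±2 weeks) after Dose 2".
- **Section 2.3:** "the remaining doses will be offered via Additional Study Visit(s) at 12 months and, if necessary, at 15 months after the first vaccine dose". This covers one-dose and two-dose participants together.
- **Section 3:** "The Additional Study Visit 1 will occur 12 months (±2 weeks) after Pre-Transplant Vaccine Visit 1". The number of visits is also fixed there: "participants who have received only one or two doses will be offered two or one Additional Study visit(s) to complete the three-dose series". The section's visit tables refer staff to Appendix B for timing.
- **Section 7.1, footnote 6:** two-dose participants "will complete an Additional Study Visit to complete the three dose vaccine series at 12 months (±2 weeks) after Pre-Transplant Vaccine Visit 1".
- **Section 7.6, scenario 2:** they "will complete their three dose vaccine series at an Additional Study Visit at 12 months (±2 weeks) after Pre-Transplant Vaccine Visit 1".
- **Appendix B:** Vaccine #3 at Additional Study Visit 1, again at month 12 (±2 weeks) from Vaccine Visit 1.

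On spacing, section 5.1 states that the vaccine "must be administered according to the following requirements". For Dose 3 these are at least 5 months from Dose 1 and at least 3 months from Dose 2. Dose 2 has a lower limit (30 days after Dose 1) and no upper limit. Section 3 allows ±2 weeks on the minimum intervals, and asks staff to try to give outstanding doses during the 12 months after enrollment.

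**The concern.** There are two separate problems.

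The first is the anchor. The same dose for the same participant has two due dates, which differ by the whole interval between Doses 1 and 2.

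The second remains once the anchor is corrected. A visit fixed by Dose 1 takes no account of when Dose 2 was given. A late Dose 2 is foreseeable, because staff are encouraged to complete doses up to month 12. In that case the month-12 visit can fall well inside the 3-month minimum, and no text says which rule prevails. A site that follows section 5.1 must hold the dose past the visit window. A site that follows the Appendix B date gives Dose 3 sooner than section 5.1 permits.

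What is at stake is a properly spaced vaccine series for these participants. The trial's endpoint is not affected.

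**Working it through.** The plan gives no figure to reproduce; this is date arithmetic.

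**Inputs and conventions.** Enrollment and Dose 1 are at the same visit (sections 7.1 and 7.3), taken as day 0. I assume 12 months = 365 days, 3 months = 91 days and 15 months = 456 days, with days converted to months by 365/12 = 30.4. The Additional Study Visit 1 window is 365 ± 14 = days 351–379. The 5-month minimum from Dose 1 is always met at that visit.

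**Step 1: do the two anchors ever agree?** With Dose 2 on day g, the Table 2 window is days g + 351 to g + 379. It overlaps days 351–379 only if g + 351 ≤ 379, so g ≤ 28. The minimum gap between Doses 1 and 2 is 30 days, so the windows never overlap when that minimum is kept. Only if the 2-week tolerance is used on it (g from 16 to 28) is there any overlap. With Dose 2 at month 6, the nominal dates are month 18 (Table 2) and month 12 (elsewhere).

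**Step 2: latest Dose 2 that still allows a month-12 Dose 3.** The limit is the visit day minus the minimum interval.

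| Visit day used | Minimum interval | Latest Dose 2 |
|---|---|---|
| 365 (nominal) | 91 | 365 − 91 = day 274 (month 9.0) |
| 379 (late edge) | 91 | 379 − 91 = day 288 (month 9.5) |
| 379 (late edge) | 91 − 14 = 77 | 379 − 77 = day 302 (month 9.9) |

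After day 302 no date meets both rules.

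**Step 3: example, Dose 2 at month 11 (day 335).**

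- Appendix B window: 351 − 335 = 16 days to 379 − 335 = 44 days after Dose 2.
- Section 5.1 minimum: 335 + 91 = day 426 (month 14.0), or 426 − 14 = day 412 (month 13.5) with the tolerance.
- Section 2.3 month-15 date: 456 − 335 = 121 days after Dose 2.
- Table 2: 335 + 365 = day 700 (month 23.0).

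**Step 4: would month 15 solve it?** Numerically, yes: 456 − 91 = day 365, so it meets the minimum for any Dose 2 up to month 12. However, section 3, section 7.6 and Appendix B give two-dose participants a single visit, at month 12.

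**Step 5: check of a rule based on the later of the two dates.**

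- Dose 2 on day 274: the two nominal dates coincide at day 365. At the early edge the gap is 351 − 274 = 77 = 91 − 14 days, which is within the section 3 tolerance.
- Dose 2 on day 335: days 426 to 426 + 28 = 454 (months 14.0–14.9).
- Dose 2 on day 365: days 456 to 484 (months 15.0–15.9).

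**The case against.** The Table 2 mismatch is not disputable: the Dose 3 row has six entries and this is clearly the fifth, so it is not an artefact of reading the PDF. The stronger objections concern the second conflict.

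- **The documents may already rank the rules.** Section 5.1 uses mandatory language. Section 3 says that, beyond the minimum intervals, no particular vaccination windows are imposed. Additional visits are offered only to finish the series, and section 2.3 mentions month 15. A site could reasonably hold the dose. This stands in part: nothing forces early dosing. But the section 3 remark sits in the paragraph on pre-transplant vaccination, four places set a ±2-week window for this visit, and the visit schedule has no month-15 slot for two-dose participants. The text leaves sites to choose.
- **Month 9 is only the nominal limit.** This is correct. The visit window covers Dose 2 up to month 9.5, and the interval tolerance extends that to month 9.9. The unavoidable conflict is confined to roughly the last two months before month 12.
- **Calling a late visit a deviation is inference.** No text says so for this visit; it follows only from the stated window.
- **The replacement rule has a small step.** With Dose 2 on day 274 it permits a 77-day gap; with Dose 2 on day 275 it requires 91 days. Both comply with section 3.
- **Materiality is low.** Agreed, and reflected in the rating.

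**Conclusion.** Both parts hold. Table 2 gives a wrong operative date for every participant in that column, most likely through a slip. Counting from Dose 1 then conflicts with the mandatory 3-month spacing: at the nominal visit if Dose 2 is after day 274, and on every possible date if it is after day 302. These limits rest on the 365/91-day convention and on Dose 1 being given at enrollment.

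The number affected cannot be derived from the documents. Section 3 describes non-transplant within 12 months with an incomplete series as uncommon. Section 4.4 expects perhaps one-third of candidates not to be transplanted in the study period, which would be 180/3 = 60 on the planned enrollment. Accrual expectations were later cut (section 13.3), and neither the share with exactly two doses nor the share with a late Dose 2 is given.

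These participants go off-study (section 8.4) and cannot contribute a post-transplant endpoint, so no result changes. The gain is a small one in participant protection. The change is optional.

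**What to change.** 1. Change the Table 2 cell in section 5.1 to count from Dose 1.
2. For two-dose participants only, state one rule in Table 2, section 3, section 7.1 footnote 6, section 7.6 scenario 2 and Appendix B: Dose 3 at month 12 from Vaccine Visit 1 (±2 weeks) or 3 months (+4 weeks) from Dose 2, whichever is later. In section 3 give this its own sentence, because the present one also covers one-dose participants, who receive Dose 2 at that visit.
3. Add the same rule to section 2.3.
4. Separately, for one-dose participants, correct Additional Study Visit 2 in two places. In section 7.1 footnote 6 change ±4 weeks to +4 weeks, as in sections 3, 5.1 and 7.6 and Appendix B; the minus side would allow 91 − 28 = 63 days between doses, below even the tolerated 77. In section 7.6 scenario 3 count the visit from Additional Study Visit 1, since the text now counts it from itself.

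The cost is wording in six places plus these two small corrections. No visit is added: the same single visit is held later for those whose Dose 2 came after month 9.
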